Statistics	The primary objective will be met by the percentage of subjects who are considered a UUI responder which is statistically superior to a performance goal of 40%. To determine responder status, the 3-day urinary voiding diary data at baseline and the 6-month follow-up visit will be used to determine daily urinary urge incontinence episodes per subject. Each subject's daily values at baseline and at 6 months will be compared to the UUI responder definition to determine if the subject is a responder. The UUI responder rate, corresponding two-

sided 95% confidence interval, and p-value from the comparison to the 40% performance goal will be calculated.

All p-values will be reported as 2-sided tests with alpha=0.05. The primary objective will be tested with a binomial test or a Z-test, depending on the use of imputation. If the primary objective is passed, the secondary objectives will each be tested using the Hochberg multiple testing strategy using a t-test or Wilcoxon signed-rank test, depending on the normality of the data.

The sample size was estimated using a binomial distribution for a one-sided alpha=0.025 test to show a 15% increase for the proportion compared to a performance goal of 40%. Assuming the alternative hypothesis of 55% of subjects who are considered an UUI responder, a minimum of 121 implanted subjects achieves at least 90% power to reject a performance goal of 40%. Sample size was computed in PASS 19.

Primary and secondary objectives will be analyzed using the Full Analysis Set (FAS). The FAS includes all subjects, using the intention-to-treat (ITT) principle, who have device implant attempted. All attempts will be made to minimize missing data. If 5% of the data or fewer are missing for the analysis, no imputation will be used, and the data will be analyzed using the Complete Case analysis set. Otherwise, if missing data are observed, multiple imputation will be used for the primary and secondary objectives. In the case of non-normal secondary objective data imputation, last observation carried forward (LOCF) imputation may be needed to test the hypothesis. Sensitivity analyses will be completed for the primary and secondary objectives including using only subjects with outcome data at baseline and follow-up ("Complete Case Analysis") and using only those complete case subjects who received stimulation ("As Treated Analysis").

[REDACTED]
[REDACTED]

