5.1.2.1 Secondary Endpoints

- Change in UUI episodes at 6 months compared to baseline in subjects with UUI at baseline
- Change in daily UF episodes at 6 months compared to baseline in subjects with UF at baseline
- Change in urinary urgency assessed through the UPS at 6 months compared to baseline
- Change in OAB-q HRQL (health related quality of life) Total Score at 6 months compared to baseline

6. Study Design

This is a prospective, multicenter, pivotal study to assess safety and efficacy for the implantable TNM device in subjects with overactive bladder.

Eligible subjects will sign a study-specific informed consent form (ICF), at which time they will be considered enrolled in the study. All eligible subjects will complete baseline procedures, including a baseline diary and assessment of medical history. Subjects must be consented and meet all inclusion and no exclusion criteria to continue to the neurostimulator implant procedure. Any subject who does

not meet all inclusion/exclusion criteria will be excluded from study participation and exited from the study.

Study requirements, including diaries, questionnaires and safety assessments will be completed as required in Section 10. Subject follow-up is expected to last approximately 24 months following the neurostimulator implant procedure. Subjects will be exited from the study after the 24-month follow-up visit is completed. Any subjects who have the device explanted and not replaced during follow-up will be exited from the study.

The study is expected to be conducted at up to 30 study sites located in the United States. Up to 200 subjects will be enrolled to obtain 121 subjects who have the study device implanted. Enrollment will be closed once the number of completed implants reaches 121; all enrolled subjects who meet eligibility criteria may be implanted (not to exceed 130 total implants).

To ensure a widespread distribution of data and minimize study site bias in study results, the maximum number of subjects to be implanted at a single study site is 24 subjects.

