If any programming changes are made during the visit, the subject will have an impedance check and sensory/motor threshold testing done with their foot in the same relaxed position as the time of implant. The subject's sensory and motor threshold will be identified using 20 hertz, 200 microseconds pulse width stimulation and titrating up amplitude until the sensory threshold, highest acceptable amplitude and motor threshold are confirmed. The neurostimulator amplitude should be set to the highest acceptable amplitude. If highest acceptable amplitude is unable to be found, it is recommended to set the amplitude to two times the motor or sensory threshold, whichever is lower. The comfort of the programmed amplitude will be verified while the subject is in expected positions and adjusted for comfort, if needed.

If the sensory threshold, highest acceptable amplitude and/or motor threshold are not observed, this will be documented. The Investigator (or delegated personnel) should try repeating the motor and sensory assessment with the foot in a different position. If the motor and/or sensory response is still not observed, the Investigator (or delegated personnel) should set neurostimulator amplitude to 3 mA unless an alternative amplitude level is recommended by the Sponsor.

The subject should have the appropriate program set based on study requirements.

Programming and device data (e.g., Usage Report, Session Report) will be collected in accordance with device instructions prior to the subject leaving the visit and transferred to Medtronic using the application on the handset and/or collected on the programming worksheet provided.

System Modification:

If the device needs to be explanted or replaced at any time after the implant procedure, a System modification procedure will be scheduled. System modifications will include device replacements and explants. Subjects will be encouraged to complete a voiding diary prior to any system modification procedure. Prior to neurostimulator removal and/or after a new neurostimulator is placed, an ultrasound image to assess measurements related to the tibial nerve may be completed.

During the visit, any relevant medication changes, procedural data, adverse events and/or device deficiencies will be collected. Sensory and/or motor thresholds should be assessed (when possible) prior to the implant procedure. Device programming (e.g., Usage Report, Session Report) will be collected in

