**Figure 1: Study Visits**

## 6. Determination of Sample Size

Sample size determination was made using PASS 2019. The sample size for the primary objective was estimated using a binomial distribution for a one-sided alpha=0.025 test to show a 15% increase for the proportion compared to a performance goal of 40%. Assuming the alternative hypothesis of  $\geq 55\%$  of subjects who are considered an UUI responder, a minimum of 121 implant attempted subjects achieves at least 90% power to reject a performance goal of 40%. The primary objective will have at least 88% power for any alternative hypothesis that is at least 15% larger than a performance goal. Secondary objectives are also expected to be adequately powered based on this sample size.

Assuming a ~40% attrition rate before implant, up to 200 subjects will be consented to achieve at least 121 subjects with implant attempted. Enrollment will be closed once the number of completed implants reaches 121; all enrolled subjects who meet eligibility criteria may be implanted (not to exceed 130 total implants). Implant attempted subjects who exit from the study will not be replaced.

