## **7.4 Handling of Missing, Unused, and Spurious Data and Dropouts**

Primary and secondary objectives will be analyzed using the FAS. The FAS includes all subjects, using the intention-to-treat principle, who have an attempted device implant. All attempts will be made to minimize missing data. For diary-based metrics, missing is defined as any diary which has a total length of less than 48 hours, as defined in section 7.2.2. The OAB-q may be missing if the HRQL Total cannot be calculated; scoring details are found in section 7.9.2.4. If 5% of the data or fewer are missing for the analysis, no imputation will be used, and the data will be analyzed using the Complete Case analysis set (Buhi 2008). Otherwise, if missing data are observed, imputation will be used for the primary and secondary objectives.

The primary objective imputation will be done using multiple imputation (MI). Predictive mean matching multiple imputation will be used for each variable. First, multiple imputation will be applied to impute missing values in average daily UUI episodes. Unless model errors dictate otherwise, each model will consider Baseline and Month 1, Month 2, Month 3, and Month 6 variables for the UUI episodes variable and demographic variables of age, gender, history of pregnancy, and BMI. The fully conditional specification (FCS) method within SAS (version 9.4 or higher) with 30 repetitions and 100 burn-in iterations will be used for imputation. No limits will be defined for imputed values. Following

imputation, the 6-month outcome data will be converted to the appropriate endpoint (i.e., change from baseline/UUI responder). The estimate and variance of the mean proportion of subjects considered a UUI responder will be determined for each imputation dataset. For the primary objective, the mean and variance for the proportion will be determined using MI analysis methods and the objective will be tested using a Z-test comparing the observed responder rate to the primary objective performance goal of 40%.

For the UUI, UF, and OAB-Q secondary objectives, the following imputation steps will be taken:

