## 7.9 Evaluation of Objectives

### 7.9.1 Primary Objective

#### 7.9.1.1 Primary Objective – UUI Responder Rate

To demonstrate that the percentage of subjects who are considered a UUI responder after 6 months of tibial neuromodulation exceeds a performance goal of 40%.

**Hypothesis:** The percentage of subjects who are considered a UUI responder 6 months after tibial neuromodulation implantation is greater than 40%.

$$H_0: p \leq 40\%$$

$$H_A: p > 40\%$$

Where  $p$  = the percentage of subjects who are UUI responders

**Endpoint Definition and Derivation:** A 3-day urinary voiding diary will be used to collect bladder symptoms, including UUI episodes. The primary objective endpoint is the proportion of tibial neuromodulation subjects considered a UUI responder at 6 months after device implant. A subject is considered a UUI responder if they meet the UUI responder criteria as defined in the voiding diary analysis section 7.2.2.

**Performance Requirements:** The null hypothesis will be rejected if the one-sided p-value is less than 0.025. Only the two-sided p-value will be reported.

**Rationale for Performance Criteria:** The proposed study design includes a primary objective performance goal of 40%. The performance goal defines an active historical control for this study and was defined to position the TNM outcome between the expected performance for medications and the more complex SNM treatment.

**Sample Size Justification:** The sample size justification for the primary objective is provided in section 6.

**Analysis Methods:** The analysis for UUI responder rate will be summarized at 6 months after implant. If 5% of the data or fewer are missing for the primary analysis, no imputation will be used, and the objective will be tested using a binomial test for the Complete Case analysis set. Otherwise, missing data will be imputed for the Full Analysis Set as specified in section 7.4, and the objective will be tested using a Z-test. The two-sided 95% confidence interval will also be provided.

**Determination of Subjects/Data for Analysis:** The primary objective analysis will include all subjects from the Full Analysis Set (i.e., all implant attempted subjects) as defined in section 7.1.3.

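### The primary analysis is called intention-to-treat over all attempted implants, but neither missing-data branch has a rule for subjects who have no device at month 6

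*SAP*

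**What the plan says.** The Full Analysis Set is all subjects with an attempted implant, analysed under the intention-to-treat principle (SAP 7.1.3, 7.2 and 7.4; Protocol 14.1.1 and 14.1.2). Failed attempts are therefore included.

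Protocol section 6 states: "Any subjects who have the device explanted and not replaced during follow-up will be exited from the study". Protocol 10.14.1 also lists not being implanted as a reason for exit, and says that no study data are collected after exit. For explants, Protocol 10.1 adds: "Subjects will be encouraged to complete a voiding diary prior to any system modification procedure".

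There are two missing-data branches:

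- **5% or fewer missing.** A binomial test is run on the Complete Case set, which SAP 7.1.3 limits to implanted subjects with baseline and follow-up outcomes.
- **More than 5% missing.** SAP 7.9.1.1 states: "Otherwise, missing data will be imputed for the Full Analysis Set as specified in section 7.4". SAP 7.4 uses predictive mean matching: "First, multiple imputation will be applied to impute missing values in average daily UUI episodes". The model holds UUI at baseline and months 1, 2, 3 and 6, plus age, gender, pregnancy history and BMI. Afterwards "the objective will be tested using a Z-test comparing the observed responder rate to the primary objective performance goal of 40" percent.

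The decision rule is: "The null hypothesis will be rejected if the one-sided p-value is less than 0.025". SAP 7.2 makes study success depend on the primary objective alone. SAP 7.9.1.1 plans a tipping-point analysis without details and sets no requirement on any sensitivity result.

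**The concern.** A subject whose implant attempt failed has only a baseline diary. Predictive mean matching gives that subject observed values from subjects still being followed, so the subject is called a responder about as often as the completers are. A subject explanted before month 6 and not replaced is imputed as if followed with the device in place, informed only by whatever month 1-3 diaries exist. A diary recorded just before explant is not a listed model variable. The Complete Case branch reaches much the same result by leaving these subjects out.

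Neither document says that loss of the device counts as non-response. The only failure-assignment analysis, in SAP 7.9.1.1, covers OAB medication and advanced therapy among complete cases. In a single-arm study with one success criterion, this bears directly on the decision: the plan can credit the device with responses in people who do not have it, under an intention-to-treat label.

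**Working it through.** **Inputs from the documents.** One-sided alpha 0.025 (SAP 7.9.1.1); performance goal 40%; n = 121 and power of at least 90% (SAP 6: "a minimum of 121 implant attempted subjects achieves at least 90% power to reject a performance goal of 40" percent); alternative 55% (Protocol Synopsis: "Assuming the alternative hypothesis of 55% of subjects who are considered an UUI responder"); 30 imputations (SAP 7.4). The 5% trigger is 0.05 × 121 = 6.05, so 7 or more missing diaries start imputation.

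**The plan's own figure.** The exact binomial test with n = 121 rejects at 60 or more responders. Its size is 2.04% at 40% and its power 90.1% at 55%. The stated 90% reproduces.

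**Assumptions, not in the documents.** Let k be the number of Full Analysis Set subjects off device at month 6, q their true response rate, and d ≥ k the total missing. Fix the true Full Analysis Set rate at 40% with device loss counted as non-response (q = 0 unless stated).

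- Rate among the others: π = (0.40 − qk/121) / (1 − k/121)
- Observed responders: X ~ Binomial(121 − d, π)
- Estimate: p = (X + d·r)/121, where r is the imputed response rate. When early diaries carry no information, r = X/(121 − d).
- Variance: V = p(1 − p)/121 + (1 + 1/30)·d·r(1 − r)/121²
- Reject if (p − 0.40)/√V > 1.96

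**Worked case, d = k = 10, q = 0.** π = 0.40 × 121/111 = 0.436. At X = 55, p = 55/111 = 0.4955, V = 0.00207 + 0.00018 = 0.00224 and Z = 0.0955/0.0474 = 2.02, so the test rejects. At X = 54, Z = 1.83 and it does not. P(X ≥ 55) for Binomial(111, 0.436) is 12.2%.

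**Size of the imputation branch**

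| Scenario | d = 8 | d = 10 | d = 12 |
|---|---|---|---|
| None off device, all missing at random | 2.5% | 2.6% | 2.7% |
| 3 off device, rest missing at random | 4.1% | 4.2% | 4.4% |
| Half off device, rest missing at random | 4.8% | 5.8% | 7.0% |
| All off device, 20% truly respond | 4.9% | 6.0% | 7.3% |
| All off device, none responds, early diaries pull r to 20% | 4.2% | 4.1% | 4.0% |
| All off device, none responds, early diaries pull r to 30% | 4.2% | 6.1% | 6.0% |
| All off device, none responds, early diaries uninformative | 8.9% | 12.2% | 16.3% |

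In the last row π is 42.8%, 43.6% and 44.4%.

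**Check by simulation.** Predictive mean matching with 30 imputations and Rubin's rules was run for 1,500 trials per scenario, with a shorter burn-in than planned and no demographic covariates. It gave 10.1% for 10 off device and 15.1% for 12. With 7 off device, 6 of them explants already doing poorly at months 1-3, it gave 4.9%. The control, 7 diaries missing at random with nobody off device, gave 2.6%. The excess therefore comes from device loss and not from imputation as such.

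**Complete Case branch.** With 6 off-device subjects dropped, 115 remain and the exact test rejects at 57 or more. π = 0.40 × 121/115 = 0.421, and P(X ≥ 57) = 6.4%.

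**After the fix.** With success at 60 of 121 and off-device subjects scored as failures, size is 2.0% for k = 0, 1.95% for k = 3, 1.8% for k = 7 and 1.65% for k = 12.

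**The case against.** Five points weigh on the other side.

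1. **The estimand.** The objective speaks of response after six months of neuromodulation in TNM subjects. That can be read as response with the device in place, and on that reading size is 2.5-2.7%. This stands as a condition on every inflated figure. It does not remove the point, because both documents also call the analysis intention-to-treat over attempted implants and neither says which target governs.
2. **The counts.** The documents give no expected number of off-device subjects at month 6. The only prior explant rate, 2.2% for migration (Protocol 11.3), is about 3 of 121, too few to trigger imputation alone. The two pausing rules in that section would let 6 + 6 = 12 explants pass, but that is a tolerance limit, not a forecast, and is not tied to month 6. This also stands.
3. **Early diaries and late explants.** Explants after month 1 normally contribute diaries to the model. Exit follows a one-month call and follow-up of related adverse events (Protocol 10.8), and sites assign diaries to visits, so some explanted subjects may have a month-6 diary. A reader might infer that no explanted subject ever has one; the documents do not establish that.
4. **Failed attempts.** Enrolment closes at 121 completed implants, so failed attempts may add to 121. With 121 implanted and 12 never implanted, the top figure is 12.5%, not 16.3%.
5. **Sensitivity analyses.** Tipping-point, All Implanted, Complete Case and As Treated analyses would show a reader the dependence. They cannot change the success decision.

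**Conclusion.** The gap is real. The plan names an intention-to-treat population and then, in both branches, handles subjects without a device as if device loss told nothing about response. If device loss counts as non-response and the true rate is 40%, the nominal 2.5% test runs at about 4-7% in moderate scenarios: 3 to 6 off-device subjects among 8-12 missing; 8-12 off-device subjects of whom 20% truly respond; or early diaries that pull imputed response to 20-30%. The Complete Case branch gives 6.4% for 6 of 121.

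A reader might infer that the test generally runs at up to 16%. The documents do not support that. The 9-16% range needs 8-12 of 121 off device, no true response among them and uninformative early diaries, all together. Nor do they support calling the analysis wrong under every target, since size is about nominal if the target is response had the device stayed in. The plan should state its target and handle device loss accordingly. This is a correction that should be made, not one that invalidates the design.

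**What to change.** Change SAP 7.4 and 7.9.1.1 and Protocol 14.1.2 and 14.4.1, for the primary endpoint and for both branches:

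- Score as UUI non-responders all Full Analysis Set subjects with no device implanted, or with the device explanted and not replaced before the month-6 diary.
- Treat these as observed outcomes that do not count toward the 5% trigger, and keep them in the analysis when the Complete Case branch applies.
- Use multiple imputation (or complete case at 5% or fewer) only for subjects with a device in place whose diary is missing.
- Keep the present imputation as a sensitivity analysis.

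The change is confined to the primary endpoint. No calculation here supports a fixed value for UUI change in these subjects, so none is proposed for the secondary endpoint.

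The cost is wording in two documents, with no new data, and a somewhat lower reported responder rate. If 55% was meant as the on-therapy rate, power falls from 90% to 84% with 3 off device, 73% with 7 and 54% with 12. If 55% was meant for the whole Full Analysis Set, power stays at 90-92%. The sponsor should say which it meant.

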14.1.2 Handling Missing Data

Primary and secondary objectives will be analyzed using the FAS. The FAS includes all subjects, using the intention-to-treat principle, who have an attempted device implant. All attempts will be made to minimize missing data. For diary-based metrics, missing is defined as any diary which has a total length of less than 48 hours, as defined in section 14.1.5. The OAB-q may be missing if the HRQL Total cannot be calculated; scoring details are found in section 14.5.4. If 5% of the data or fewer are missing for the analysis, no imputation will be used and the data will be analyzed using the Complete Case analysis set²⁵. Otherwise, if missing data are observed, imputation will be used for the primary and secondary objectives.

The primary objective imputation will be done using multiple imputation (MI). Predictive mean matching multiple imputation will be used for each variable. First, multiple imputation will be applied to impute missing values in average daily UUI episodes. Unless model errors dictate otherwise, each model will consider Baseline and Month 1, Month 2, Month 3, and Month 6 variables for the UUI episodes variable and demographic variables of age, gender, history of pregnancy, and BMI. The fully conditional specification (FCS) method within SAS (version 9.4 or higher) with 30 repetitions and 100 burn-in

iterations will be used for imputation. No limits will be defined for imputed values. Following imputation, the 6-month outcome data will be converted to the appropriate endpoint (i.e., change from baseline/UUI responder). The estimate and variance of the mean proportion of subjects considered a UUI responder will be determined for each imputation dataset. For the primary objective, the mean and variance for the proportion will be determined using MI analysis methods and the objective will be tested using a Z-test comparing the observed responder rate to the primary objective performance goal of 40%.

For the secondary objectives, the following imputation steps will be taken:

- For secondary objectives related to UUI episodes, the imputation datasets created for the primary objective will be used. For OAB-q HRQL, UF episodes, and urgency, a new set of imputation datasets will be created following the same methods as the primary objective but replacing UUI episodes with OAB-q HRQL, UF episodes, or urgency score.

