- After imputation, the normality for the outcome metric will be checked through Shapiro-Wilk test for each imputation dataset. If $p\text{-value} > 0.05$ for at least 15 imputed datasets (half of the total), it will be considered that the data are normally distributed. In this case, the mean and standard error of the outcome metric will be calculated within each imputed dataset, and then combined using MI analysis methods. The mean and standard error of the outcome metric will be reported, and the objective will be tested with a t-test.
- If the distribution of outcome metric is non-normal ($p\text{-values} \leq 0.05$ in more than 15 of the imputed datasets), MI will not be used. Instead, last observations carried forward (LOCF) will be applied, with the imputed dataset tested using the Wilcoxon signed-rank test.

Sensitivity analyses will be completed for the primary and secondary objectives including subjects who received a TNM implant (“All Implanted Analysis”), using only subjects with outcome data at baseline and follow-up (“Complete Case Analysis”), and using only those complete case subjects who received stimulation (“As Treated Analysis”).

Comprehensive descriptions of subject accountability and missing data will be provided.

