- For secondary objectives related to UUI episodes, the imputation datasets created for the primary objective will be used. For OAB-q HRQL and UF episodes, a new set of imputation datasets will be created following the same methods as the primary objective but replacing UUI episodes with OAB-q HRQL or UF episodes. For OAB-q HRQL, the imputation model contains HRQL scores only at those visits where the assessment was collected (Baseline, Month 3, Month 6). Constraints will be set so that the imputed OAB-q HRQL are restricted to values ranging from 0-100. If the MI procedure is unable to successfully impute values within that range, the constraints will be applied after imputation, such that any values less than 0 will be set to 0, and any values greater than 100 will be set to 100.
- After imputation, the normality for the outcome metric will be checked through Shapiro-Wilk test for each imputation dataset. If  $p\text{-value} > 0.05$  for at least 15 imputed datasets (half of the total), it will be considered that the data are normally distributed. In this case, the mean and standard error of the outcome metric will be calculated within each imputed dataset, and then combined using MI analysis methods. The mean and standard error of the outcome metric will be reported, and the objective will be tested with a t-test.
- If the distribution of outcome metric is non-normal ( $p\text{-values} \leq 0.05$  in more than 15 of the imputed datasets), MI will not be used. Instead, last observations carried forward (LOCF) will be applied, with the imputed dataset tested using the Wilcoxon signed-rank test.

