For the secondary objective related to urgency using the UPS, the imputation datasets will be created using multiple imputation (MI). Logistic regression multiple imputation will be used for each variable which accounts for the ordinal nature of the UPS. First, multiple imputation will be applied to impute missing values in UPS. Unless model errors dictate otherwise, each model will consider Baseline, Month 3, and Month 6 variables for the UPS variable and demographic variables of age, gender, history of pregnancy, and BMI. The fully conditional specification (FCS) method within SAS (version 9.4 or higher) with 30 repetitions and 100 burn-in iterations will be used for imputation. Imputed values will be required to be 1, 2, or 3 to match the original scale. After imputation, the mean and standard error of the change from Baseline to Month 6 in UPS will be calculated within each imputed dataset, and then combined using MI analysis methods. The mean and standard error will be reported, and the objective will be tested with a t-test.

Sensitivity analyses will be completed for the primary and secondary objectives including subjects who received a TNM implant (“All Implanted Analysis”), using only subjects with outcome data at baseline

and follow-up (“Complete Case Analysis”), and using only those complete case subjects who received stimulation (“As Treated Analysis”).

[REDACTED] Comprehensive descriptions of subject accountability and missing data will be provided.

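### Above 5% missing, a Shapiro-Wilk vote replaces multiple imputation with LOCF for UUI, UF and OAB-q change; keep and pool the imputations, as SAP 7.4 already does for UPS

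*SAP*

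**What the plan says.** SAP 7.4 has two branches. At 5% missing or less, complete cases are analysed without imputation. Above that, 30 imputed datasets are made for UUI, UF and OAB-q change, and Shapiro-Wilk is run in each. If p exceeds 0.05 in at least 15, the mean and SE are pooled and tested with a t-test. If p is 0.05 or less "in more than 15 of the imputed datasets), MI will not be used". The replacement is: "Instead, last observations carried forward (LOCF) will be applied, with the imputed dataset tested using the Wilcoxon signed-rank test". Protocol 14.1.2 has the same fallback ("Instead, last observations carried forward (LOCF) will be applied").

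Three neighbouring rules matter:

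- **UUI shares its imputations with the primary.** "For secondary objectives related to UUI episodes, the imputation datasets created for the primary objective will be used". For the primary there is no normality check: "the objective will be tested using a Z-test comparing the observed responder rate" with the 40% goal.
- **UPS is treated differently in the SAP.** "Logistic regression multiple imputation will be used for each variable which accounts for the ordinal nature of the UPS". After pooling, "The mean and standard error will be reported, and the objective will be tested with a t-test". There is no vote and no LOCF.
- **The Protocol puts UPS on the voted route.** "For OAB-q HRQL, UF episodes, and urgency, a new set of imputation datasets will be created" by the primary's method, so the vote and LOCF apply to it there.

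**The concern.** The rule is pre-specified and mechanical, so data-driven choice is not the complaint. The problem is what it decides. Non-normal change is a reason to consider another test. It says nothing about whether a missing month-6 value is better represented by draws from a model or by copying an old visit. One vote changes the imputation, the test and the quantity tested, although the hypotheses in SAP 7.9.2.1, 7.9.2.2 and 7.9.2.4 concern the change μ, which is powered as a mean.

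Consequences:

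- UUI response could rest on multiple imputation (MI) while UUI change rests on LOCF, for the same subjects.
- LOCF treats copied values as observed. The SAP does not say whether baseline is carried when no later value exists. That can arise, because the Full Analysis Set includes subjects whose implant was attempted but failed. For OAB-q the only post-baseline value available to carry is month 3.
- No sensitivity analysis in the visible text restores the pooled MI result once LOCF is chosen.

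UF change matters most, because SAP 7.5 makes it the evidence for the frequency part of the OAB indication.

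**Working it through.** **1. The plan's own power figures.** Inputs are the means, SDs and sample sizes in SAP 7.9.2.1, 7.9.2.2 and 7.9.2.4. Power comes from the noncentral t distribution with noncentrality (mean/SD)×√n.

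- UUI: (2.0/3.5)×√121 = 6.29; power 99.99% at alpha 0.013 (plan: at least 99%).
- UF: (2.0/3.0)×√51 = 4.76; power 98.3% at 0.013 and 99.7% at 0.05 (plan: at least 98%).
- OAB-q: (20/30)×√121 = 7.33; power above 99.9% (plan: at least 99%).

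All three reproduce.

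**2. The trigger.** 6/121 = 4.96% (not imputed) and 7/121 = 5.79% (imputed). For UF, 2/51 = 3.92% and 3/51 = 5.88%.

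**3. How often the vote picks LOCF.** The documents give no distribution shape, so it is assumed.

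| Endpoint | Assumed model | Chance of LOCF |
|---|---|---|
| UUI | normal, SD 3.5 | 0.04–0.07 |
| UUI | homogeneous counts (250 trials) | 0.23–0.27 |
| UUI | gamma-Poisson counts, SD 2.25 | 0.84–0.88 |
| UUI | gamma-Poisson counts, mean −2.01, SD 3.52 | 0.996–1.00 |
| UF | counts, mean −1.97, SD 3.04 | 0.05–0.12 |
| UF | continuous, skewness 1 | 0.70–0.80 |
| OAB-q | other models (250 trials) | 0.04–0.14 |
| OAB-q | limited to 0–100, mean 19.8, SD 29.9 | 0.39–0.49 |

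Skewed UUI change is plausible, since entry needs at least 3 episodes in 72 hours and counts cannot fall below zero.

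**4. How far the estimate moves.** Count and bounded-score models, 500 trials per setting. Assumptions: 60/85/95/100% of the effect at months 1/2/3/6, monotone random dropout, first missed visit uniform, baseline carried if nothing later exists. MI used 30 predictive-mean-matching datasets without demographic covariates. The planned SEs are 3.5/√121 = 0.32, 3.0/√51 = 0.42 and 30/√121 = 2.7.

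| Endpoint | Missing | Less improvement with LOCF than MI | Divided by planned SE |
|---|---|---|---|
| UUI | 7/121 | 0.05–0.06/day | about 0.2 |
| UUI | 10/121 | 0.07–0.09/day | 0.2–0.3 |
| UUI | 18/121 | 0.13–0.15/day | 0.4–0.5 |
| UF | 3/51 | 0.04/day | 0.1 |
| UF | 8/51 | 0.12/day | 0.3 |
| OAB-q | 7/121 | 0.6 points | 0.2 |
| OAB-q | 18/121 | 1.5 points | 0.6 |

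MI stayed within 0.05/day (UUI), 0.03/day (UF) and 0.04 points (OAB-q) of the full-data result. A separate gamma-Poisson model (SD about 3.6–3.7) gave UUI shifts of 0.08 at 7/121 and 0.17 at 18/121.

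Dropout timing drives the size. At 18/121 the UUI shift is 0.02–0.04 if every dropout has a month-3 value, and 0.31–0.34 if none has any follow-up. By hand, subjects carried at zero change cost 18/121 × 2.0 = 0.30.

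The direction depends on the trajectory. With skewness 1, about 19% missing and a true mean of −2.0, LOCF gave −1.85 when the effect was growing and −2.11 when it was waning. Pooled MI gave −2.02 in the growing case.

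**5. Effect on the test.** In the step 4 models, significance at 0.0125 differed by at most 0.2 percentage points (UUI, OAB-q) and 1.0 point (UF). In the skewness-1 model with about 19% missing, a growing effect and more dropout among subjects doing worse at month 1, UF power was 99% with pooled MI and 93% with LOCF plus Wilcoxon.

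With no mean effect at 6 months after a benefit that wanes, and about 10% missing, UUI type I error at 0.05 was 5.4% with pooled MI and 12.8% with LOCF plus Wilcoxon. Much of that excess comes from Wilcoxon, not LOCF. On complete data with skewness 1 and mean change 0, Wilcoxon rejects 15.6% (n=121) and 8.9% (n=51), against 5.1% and 5.5% for the t-test.

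**6. UPS.** Eleven distributions on −2 to 2 with mean 0.5 and SD 0.8, n=121, failed Shapiro-Wilk in every simulated trial. The Protocol's route would virtually always send UPS to LOCF; SAP 7.4 never does.

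**The case against.** The Protocol synopsis gives a reason: with non-normal data, LOCF may be needed so that the hypothesis can be tested. A signed-rank test has no mean and SE to pool, so a single completed dataset is a crude but coherent fallback. That explains the rule without justifying it. The stated parameter is a mean change, and a pooled t-test is available.

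SAP 7.4 promises a mean and SE only in the normal branch, so no text says that an LOCF mean will be the headline estimate. This stands in part: what is reported after the switch is unspecified, which is also a gap.

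The shifts just above the trigger are small, about 0.1 to 0.2 of a planned SE, and the larger ones need missing rates or dropout timing that the documents do not give. That stands, as does the wide spread in the chance of switching.

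The remedy has limits:

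- MI assumes missing at random. With 18/121 missing and weighted to poorer early responders, MI erred toward benefit (UUI 0.02–0.08/day, OAB-q 1.0 point), while baseline-carried LOCF erred toward no effect (UUI 0.07–0.10/day, OAB-q 0.6 points).
- The pooled t-test's simulated level was 0.048–0.056 at 0.05 and 0.013–0.018 at 0.0125. On complete data with n=51 and skewness 2, the t-test reached 6.6% and 2.5%.

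Planned complete-case analyses help, but they do not bring back the pooled MI estimate.

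On UPS, the Protocol leaves detail to the SAP. Section 7.12 of the SAP is listed in its contents but is absent from the text available here, so the departure may be recorded there. UPS is also an imperfect precedent, because the Wilcoxon sentence in SAP 7.9.2.3 is not expressly limited to the non-imputed branch.

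**Conclusion.** The concern holds and should be corrected. Above 5% missing, distribution shape alone can move up to three confirmatory secondaries from MI to LOCF, and UUI change can part company with the primary that uses the same imputations. For UUI, where skewed change is plausible, the switch is likely: 0.84 to 1.00 in the gamma-Poisson models, against 0.04 to 0.07 if change is normal.

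The consequence is limited. Study success rests on the primary (SAP 7.2), which is unaffected, and significance at the planned effects changes little in most settings. The harm is to the estimate, its SE and the coherence of the two UUI results. For UUI it is 0.05–0.15/day in the main count models with uniform dropout timing, and about 0.3/day if 18 of 121 subjects have no follow-up and baseline is carried. Shape, missing rate, dropout timing, trajectory and the baseline-carry rule are assumptions, so confidence in the size is moderate. The UPS difference between the documents is a lesser point.

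**What to change.** 1. Delete the normality vote and LOCF switch from SAP 7.4 and Protocol 14.1.2. For all four secondaries with more than 5% missing, keep the 30 imputations, pool mean change and SE by Rubin's rules, and use the t-test.
2. State that the Shapiro-Wilk/Wilcoxon sentence in SAP 7.9.2.1–7.9.2.4 and Protocol 14.5.1–14.5.4 applies only when nothing is imputed.
3. Report a complete-case Wilcoxon as supportive on both sides of the 5% line. The main test for non-normal data would still differ between 6/121 and 7/121 missing, and this covers it. For UF, if change is strongly skewed, a rank or bootstrap analysis within the imputations is a sensible addition.
4. Keep LOCF, if at all, as a sensitivity analysis with its carry rule stated. Its bias ran opposite to MI's under the informative dropout tested, so the pair is informative. The tipping-point analysis planned for the primary could be extended to the secondaries.
5. Align the Protocol's UPS text with SAP 7.4, or record the departure if section 7.12 does not already do so.

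The cost is SAP wording, matching Protocol text or a recorded departure, and less programming for the main analysis. The main statistical price is a test more sensitive to extreme diaries, which item 3 addresses.
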